9. ASSESSMENT OF SAFETY

9.1 METHODS AND TIMING FOR ASSESSING, RECORDING, AND ANALYZING SAFETY PARAMETERS

9.1.1 ADVERSE EVENTS

ICH E6 defines an AE as any untoward medical occurrence in a subject or clinical investigation subject administered a pharmaceutical product regardless of its causal relationship to the study treatment. An AE can therefore be any unfavorable and unintended sign (including an abnormal laboratory finding), symptom, or disease temporally associated with the use of a medicinal (investigational) product, whether or not considered related to the medicinal (investigational) product.

The occurrence of an AE may come to the attention of study personnel during study visits and interviews of a study subject presenting for medical care, or upon review by a study monitor.

The period of observation for which AEs are to be collected begins after the subject has signed the ICF, throughout the study intervention period, and for 28 days post treatment.

All AEs, whether reported by the subject or noted by study personnel, will be recorded in the subject's medical record and captured on the appropriate CRF.

Information to be collected includes event description, time of onset, Investigator's assessment of severity, Investigator's assessment of relationship to study drug, and time of resolution/stabilization of the event. All AEs occurring while on study must be documented appropriately regardless of relationship to study drug. All AEs will be followed to adequate resolution as per [Section 9.3 TYPE AND DURATION OF FOLLOW-UP OF SUBJECTS AFTER ADVERSE EVENTS](#).

Any medical condition that is present at the time that the subject is screened will be considered as baseline and not reported as an AE. However, if the condition deteriorates at any time during the study, it will be recorded as an AE. All AEs must be graded for intensity and relationship to study drug.

9.1.2 INTENSITY OF EVENT

All AEs will be assessed by the Investigator according to NCI-CTCAE, Version 4.0. For any AE that is not specifically covered in NCI-CTCAE, Version 4.0, the criteria from

Table 1 should be used:

Table 1: Description of Grades According to the CTCAE	
Grade	Description
0	No AE or within normal limits
1	Mild; asymptomatic or mild symptoms; clinical or diagnostic observations only; intervention not indicated
2	Moderate; minimal, local, or non-invasive intervention indicated; limiting age-appropriate instrumental activities of daily living
3	Severe or medically significant but not immediately life-threatening; hospitalization or prolongation of hospitalization indicated; disabling; limiting self-care activities of daily living
4	Life threatening consequences; urgent intervention indicated
5	Death related to AE

If the intensity changes within a day, the maximum intensity should be recorded. If the intensity changes over a longer period of time, the changes should be recorded as separate events (having separate onset and stop dates for each change in intensity). Changes in the intensity of an AE will be documented to allow an assessment of the duration of the event at each level of intensity to be performed. AEs characterized as intermittent require documentation of onset and duration of each episode.

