Statistical Considerations:	
This is a proof of concept feasibility study, so no power calculation is needed. Therefore, up to 35 subjects meeting inclusion/exclusion criteria will be recruited until 30 subjects have completed treatment. Descriptive statistics will be performed to explore changes in primary and secondary outcomes measures between baseline and end of treatment. The primary efficacy measure will be a reduction in the number of stress incontinence episodes/day. Secondary efficacy measures will include reduction in number of voids per day, volume of voids, 24 hour pad weight, responses to validated questionnaires, changes in UPP measures, changes in sexual function, and changes in pelvic floor muscles as measured by MRI.
 
Safety will be determined by the number and type of adverse events reported during treatment. Various imputation methods may be explored.

Study Intervention/Treatment:	
Participation in this study includes 5 in person study visits and two telephone and/or mailed questionnaire visits. Additional in person and/or telephone visits may be added as needed.
 
Study subjects will receive 3 mg of GTx-024 orally daily.

Table 1. Schedule of Measures.

	Screening Visit Days -21-0	Additional Screening Days -21-0	Visit 1. Baseline³ Week 0	Visit 2. Week 1 ± 3 days	Visit 3. Week 4 ± 3 days	Visit 4. Week 8 ± 3 days	Visit 5. Week 12 ± 3 days	Visit 6. Week 16 ± 7 days
	Clinic Visit	Clinic Visit	Clinic Visit	Phone Call	Clinic Visit	Clinic Visit	Clinic Visit	Phone Call and Mail
Consent	x							
Inclusion/Exclusion	x		x					
History			x					
Interview/Vital Signs	x		x		x	x	x	
Height/Weight	x				x	x	x	
24 hour Pad Weight	Instruct		x		x	x	x	
3 day Voiding Diary	Instruct		x		x	x	x	
Serum AST, ALT, Total Bilirubin	x				x	x	x	
Serum FSH ¹ ,	x							
CBC			x				x	
UA Dipstick (with culture as needed)	x		x				x	
Lipid Panel			x				x	
Testosterone Levels			x				x	
SHBG			x				x	
UPP			x				x	
Pelvic MRI		x					x	
Bladder Stress Test	x						x	
Mammogram ²		x						
Begin Daily ⁴ Treatment			x					
End Treatment							x	
Concomitant Meds	x		x	x	x	x	x	x
Adverse Events			x	x	x	x	x	x
HIV, Hep A, B, C Testing	x							
UDI-6; IIQ			x		x	x	x	x
PGI-S			x		x	x	x	x
MESA Questionnaire	x				x	x	x	x
PGI-I					x	x	x	x
FSFI Questionnaire			x		x	x	x	x
Bladder Scan PVR			x		x	x	x	
Ciprofloxacin 500 mg po (or equivalent)			x				x	
Focused Physical Exam			x				x	

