2.2 RISKS ANALYSIS AND RISK ASSESSMENT

2.2.1 POTENTIAL ANTICIPATED ADVERSE EVENTS

An adverse event is any clinical event that impacts, or that has the potential to impact, the health or safety of a Clinical Study subject caused by or associated with the study device and/or testing. Assessment for potential adverse events will be ongoing throughout this trial.

The benefits of treatment may include improvement in the frequency, or severity of urine loss, and improvement in quality of life. Decreases in serum triglycerides, cholesterol, and body fat, and improvements in insulin resistance, lean body mass and physical endurance are also possible benefits.

Adverse event tables and serious adverse events discussed below and are presented separately by adverse events reported among healthy volunteers on a single trial of 86 days of GTx-024 3 mg versus placebo and those enrolled on cancer trials of at least 86 days exposure to GTx-024 3 mg or placebo.

Adverse events reported among > 5% of GTx-024 3mg treated healthy subjects
Percentage of subjects reporting a given adverse event at least once

Primary System Organ Class	Preferred Term	GTx-024 N=24	Placebo N=24
Gastrointestinal disorders	Diarrhea	8.3	12.5
	Dyspepsia	8.3	8.3
	Vomiting	8.3	0.0
General disorders and administration site conditions	Vessel puncture site bruise	12.5	4.2
	Fatigue	8.3	8.3
	Malaise	8.3	0.0
Infections and infestations	Herpes simplex	8.3	0.0
Injury, poisoning and procedural complications	Contusion	8.3	4.2
Investigations	Alanine aminotransferase increased	20.8	0.0
Musculoskeletal and connective tissue disorders	Back pain	12.5	16.7

Primary System Organ Class	Preferred Term	GTx-024 N=24	Placebo N=24
Nervous system disorders	Headache	20.8	20.8
	Dizziness	12.5	4.2
Respiratory, thoracic and mediastinal disorders	Pharyngolaryngeal pain	12.5	12.5

No serious adverse events (SAEs) were reported on this trial.

These side effects are based on information obtained from a clinical study (G200501) administering GTx- 024 3 mg for 86 days in healthy subjects– elderly males and postmenopausal females. Studies suggest that side effects associated with the study drug resolve after GTx-024 is stopped.

**Adverse events reported among > 5% of GTx-024 3 mg treated cancer subjects
Percentage of subjects reporting a given adverse event at least once**

Primary System Organ Class	Preferred Term	GTx-024 N=432	Placebo N=378
Blood and lymphatic system disorders	Anemia	34.7	34.7
	Neutropenia	18.3	23.3

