	Thrombocytopenia	10.4	10.8
	Leukopenia	8.3	9.0
Gastrointestinal disorders	Nausea	34.7	34.9
	Vomiting	20.1	21.2
	Constipation	12.3	10.1
	Diarrhea	11.6	12.7
General disorders and administration site conditions	Abdominal pain	5.1	3.7
	Fatigue	15.7	16.7
	Asthenia	15.3	13.5
	Disease progression	11.8	16.7
Infections and infestations	Pyrexia	10.2	9.8
	Pneumonia	5.6	7.1
Investigations	Blood creatinine increased	8.1	5.0

Primary System Organ Class	Preferred Term	GTx-024 N=432	Placebo N=378
	Weight decreased	6.0	4.8
Metabolism and nutrition disorders	Decreased appetite	10.6	14.8
Musculoskeletal and connective tissue disorders	Arthralgia	8.1	7.9
	Pain in extremity	5.6	4.2
Nervous system disorders	Headache	7.4	6.1
	Peripheral sensory neuropathy	5.8	3.4
	Dizziness	5.6	6.3
Respiratory, thoracic and mediastinal disorders	Dyspnoea	12.3	7.4
	Cough	9.5	9.3
Skin and subcutaneous tissue disorders	Alopecia	17.8	18.5

Serious adverse events (SAEs) reported among > 2% of GTx-024 3 mg treated cancer subjects

Percentage of subjects reporting a given serious adverse event at least once

Primary System Organ Class	Preferred Term	GTx-024 N=432	Placebo N=378
Blood and lymphatic system disorders	Anemia	4.2	3.7
	Neutropenia	3.2	3.7
	Febrile neutropenia	2.3	1.6
Blood and lymphatic system disorders	Thrombocytopenia	2.3	1.6
General disorders and administration site conditions	Disease progression	7.9	11.9
Infections and infestations	Pneumonia	3.5	3.2
Neoplasms benign, malignant and unspecified (incl cysts and	Malignant neoplasm progression	2.8	2.1

An AE that appears related to GTx-024 in clinical trials has been a dose-dependent, transient, asymptomatic increase in ALT. However, these increases were modest at doses up to 10 mg per day. Most of the subjects studied to date had ALT levels that

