10. STATISTICAL CONSIDERATIONS

Since this is a proof of concept feasibility study, no power calculation is needed. Based on Dalton, 2011, 10-20% of patients may withdraw from the study before completing treatment. Therefore, we will recruit up to 35 patients meeting inclusion/exclusion criteria until 30 subjects have completed treatment. Descriptive statistics will be used to explore changes in primary and secondary outcomes measures between baseline and end of treatment. Although the primary efficacy measure will be a change in frequency of daily stress leaks between Baseline and Week 14 weeks, response to treatment will also consider secondary efficacy measures (change in frequency of voids per day, urine volume per void, change in 24 hour pad weight, responses to validated questionnaires, changes in UPP measures, changes in sexual function), and change in pelvic floor muscles as measured by MRI. Safety will be reported by the number and type of adverse events reported during treatment. No imputations for missing data will be conducted. There will be no adjustment for multiple testing.

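### Safety is summarised as a count of adverse events, but each lasting change of intensity is recorded as a new event, so the count can exceed the number of women affected

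*Combined protocol and SAP*

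**What the plan says.** Section 9.1.2 sets the recording rule. Within one day only the worst grade is kept: "If the intensity changes within a day, the maximum intensity should be recorded". When intensity changes over a longer period, "the changes should be recorded as separate events (having separate onset and stop dates for each change in intensity". The section gives the reason: "Changes in the intensity of an AE will be documented to allow an assessment of the duration of the event at each level of intensity". It also asks for the onset and duration of each episode of an intermittent event.

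The summary measure is one sentence in Section 10: "Safety will be reported by the number and type of adverse events reported during treatment". The synopsis uses the same unit: "Safety will be determined by the number and type of adverse events reported during treatment". Section 10.1 sets out methods endpoint by endpoint for efficacy and gives none for safety. No section defines a safety population, a denominator, a subject-level incidence or a maximum-grade rule.

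The earlier GTx-024 rates in Section 2.2.1 are in another unit: "Percentage of subjects reporting a given adverse event at least once". In the table for healthy subjects, the row "Alanine aminotransferase increased" shows 20.8% on GTx-024 3 mg and 0.0% on placebo, with 24 subjects in each group. The same section identifies ALT as the drug-related signal: "An AE that appears related to GTx-024 in clinical trials has been a dose-dependent, transient, asymptomatic increase in ALT".

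**The concern.** The recording rule and the summary measure are each reasonable alone, but nothing joins them. An episode that moves from grade 1 to grade 2 and back to grade 1 over several days gives three event records. Under Section 10, read literally, it contributes three to the reported number. That number then depends partly on how often grades changed, and not only on how many women were affected.

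Describing the safety profile of GTx-024 3 mg is a stated objective, and the study has one arm. A reader will naturally set the results beside the Section 2.2.1 tables, because the protocol offers no other reference rates. A count of events cannot be read directly against a percentage of subjects.

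**Working it through.** **Inputs**
- Reference ALT rate: 20.8% of 24 subjects (Section 2.2.1, healthy-subject table).
- Sample size: up to 35 enrolled, aiming for 30 completers (Section 10).
- Scheduled on-treatment ALT draws: 3, at Weeks 4, 8 and 12 (Schedule of Measures in the synopsis). ALT must be within normal limits at entry (Section 5.1).
- Records per affected woman, r: not given in the documents. Assumed to lie between 1 and 3, since three scheduled draws can show at most three different successive grades.

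**Step 1: unit of the reference rate.** 5/24 = 20.8%, which reproduces the tabulated figure. The other percentages in that table are also whole numbers of subjects out of 24: 1/24 = 4.2%, 2/24 = 8.3%, 3/24 = 12.5%, 4/24 = 16.7%. The unit is therefore the subject.

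**Step 2: women expected to be affected at the same risk.** N × 5/24:
- 35 × 5/24 = 7.3
- 30 × 5/24 = 6.3

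**Step 3: expected event count under the recording rule.** N × 5/24 × r, with N = 35:

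| Mean records per affected woman | Events in 35 women | Events per 100 women |
|---|---|---|
| 1 (no grade change in anyone) | 7.3 | 20.8 |
| 1.5 (a quarter have 3 records, the rest 1) | 10.9 | 31.3 |
| 2 (half have 3 records, half 1) | 14.6 | 41.7 |
| 3 (everyone affected has 3 records) | 21.9 | 62.5 |

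The underlying risk is the same in every row. With N = 30, the range is 6.3 to 18.8 events.

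The bottom row needs every affected woman to have an abnormal ALT at all three draws, with a different grade at each successive draw. It is a ceiling for scheduled draws; unscheduled draws could add records.

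**Step 4: reading a reported count backwards.** With at most 3 records per woman, E events come from between E/3 and E women. For a report of 21 ALT events in 35 women, that is 21/3 = 7 women (7/35 = 20%) up to 21 women (21/35 = 60%). The planned summary does not distinguish these.

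**The case against.** The strongest reply is that the documents do not show ALT being multiplied. A reader might infer that the main known risk will be counted several times per woman. That does not follow. A rise that stays at one grade and then returns to normal is one record, because the grade table in Section 9.1.2 places values within normal limits at grade 0. Section 2.2.1 describes the rises as modest, reports that most subjects stayed within normal limits, and says levels returned to normal in most cases with continued dosing. Transient is not the same as moving between grades, and no frequency of grade change is given. The true count may lie close to the lower end of the range.

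A reader might also infer that the trial cannot be compared with the earlier rates. That too is unsupported. Section 9.1.1 has each event captured on the subject's CRF with its onset, severity and resolution, so the number of women with at least one event can be derived. The plan does not ask for it. Nor does the protocol promise a formal comparison: the Section 2.2.1 tables are background risk information, and the exact 95% interval for 5/24 is about 7% to 42%, a weak yardstick in any unit.

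Nor is the recording rule an error. It has a stated purpose, duration at each intensity, and total duration still follows from first onset to last stop. Finally, the Section 10 sentence is brief and does not exclude subject-level tables.

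All of this stands, and it limits the point to the summary measure. It does not supply the missing rule. The one safety statistic named is a number of events, and the protocol defines split records as separate events.

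**Conclusion.** The point holds as a gap in how safety is to be summarised, located in Section 10 and the synopsis. Followed as written, the event count can exceed the number of episodes and of women affected, and its unit differs from that of the protocol's only reference rates. In the ALT illustration, the same 7.3 expected women give between 7.3 and 21.9 events. That range rests on two assumptions: that the earlier 20.8% applies here, and that each affected woman has 1 to 3 records. The upper end is a ceiling and not a forecast.

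The weight is modest. The primary endpoint, the sample size and the data collected are unaffected, and the gap can be closed before analysis. It is still worth closing, because it leaves a stated objective without a defined unit.

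**What to change.** Leave the recording rule in Section 9.1.2 as it is. In Section 10 and the synopsis, replace the safety sentence with wording such as: Adverse events will be summarised as the number and percentage of treated subjects with at least one event, by preferred term, each subject counted once per term at maximum grade. Event counts will be shown as a supplement, with consecutive grade-change records of one episode collapsed to a single event running from the first onset to the last stop date.

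Distinct episodes of an intermittent event would remain separate in the supplementary count. The subject-level table needs no change to the CRF.

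The cost is a few sentences in two places and slightly more tabulation. No new data or visits are required.

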9.1.3 DRUG – ADVERSE EVENT RELATIONSHIP

Classification of Relationship/Causality of Adverse Events (AE/SAE) to study drug: The investigator will determine the relationship between the study drug administration and the occurrence of an AE/SAE as defined below:

Not Related: The temporal relationship of the adverse event is determined to be Not Related to study drug administration.

Possibly Related: The temporal relationship of the adverse event to study drug administration makes a causal relationship possible. Other medications, therapeutic interventions, or underlying conditions provide a probable explanation for the observed event.

Probably Related: The temporal relationship of the adverse event to study drug administration makes a causal relationship.

Probable: Other medications, therapeutic interventions or underlying conditions provide a possible explanation for the observed event.

Related: The temporal relationship of the adverse event is determined to be Related to study drug administration.

Unable to Determine: The temporal relationship of the adverse event to study drug administration makes a causal relationship unable to determine or unknown.

9.1.4 SERIOUS ADVERSE EVENTS

An SAE is defined as an AE that meets one of the following conditions:

- Death
- Life-threatening event (defined as a subject at immediate risk of death at the time of the event)
- An event requiring inpatient hospitalization or prolongation of existing hospitalization
- Results in congenital anomaly or birth defect
- Results in a persistent or significant disability/incapacity
- Any other important medical event that may not result in death, be life threatening, or require hospitalization, may be considered a serious adverse experience when, based upon appropriate medical judgment, the event may jeopardize the subject and may require medical or surgical intervention to prevent one of the outcomes listed above. Examples of such medical events include allergic bronchospasm requiring intensive treatment in an emergency room or at home, blood dyscrasias or convulsions that do not result in inpatient hospitalization, or the development of drug dependency or drug abuse

All SAEs will be:

- Recorded on the appropriate CRF
- Reported to the designated Safety department/pharmacovigilance contractor using a SAE Report Form within 24 hours of awareness
- Followed through to resolution by a study Investigator
- Reviewed and evaluated by a study Investigator

9.2 REPORTING PROCEDURES

9.2.1 SERIOUS ADVERSE EVENTS

All SAEs, including death due to any cause, which occur after the subject signs the ICF and within 28 days following the last administration of study drug, whether or not related to the study drug, must be reported immediately to the designated Safety Department/pharmacovigilance contractor within **24 hours** by e-fax, e-mail, or telephone (see contact information below). At the very least, the following information must be reported:

- Date and time of report
- Reporter's name and phone number
- Investigator's name and site number
- Subject number
- SAE information: event term, onset date, causal relationship
- Study drug: start date of study drug and whether or not study drug has been withheld or discontinued

SAE Reporting Contact Information:

US Safety Toll-Free E-Fax Line: **[name]**

US Safety Toll-Free Unmanned [contact]**

Safety E-mail: [contact]

Information about all SAEs is collected and recorded on the SAE Report Form. The Investigator must assess the relationship of any SAE to study drug, complete the SAE Report Form, and send the completed, signed form by e-fax or e-mail within 24 hours to the assigned drug safety group. As a back-up, the site may report SAEs using the unmanned safety hotline, with a completed SAE Report Form forwarded to the assigned drug safety group within 24 hours following notification on the hotline. The original copy of the SAE Report Form and the e-fax confirmation sheet must be kept with the case report form documentation at the study site.

Follow-up information must also be sent to the same assigned drug safety group by e-fax or e-mail using either a new SAE Report Form stating that this is a follow-up to the previously reported SAE (giving the date of the original report), or by using a follow-up query form.

If an SAE is not previously documented (new occurrence) in the Investigator's Brochure (IB) and is thought to be related to the relevant Investigational Medicinal Product (IMP), the assigned drug safety group may urgently require further information from the Investigator for Regulatory Authority reporting. The drug safety group may need to issue an Investigator Notification (IN) to inform all Investigators involved in any study with the same drug that this SAE has been reported. Suspected Unexpected Serious Adverse Reactions (SUSARs) will be collected and reported to the regulatory/competent

authorities and relevant IRBs/IECs in accordance with Food and Drug Administration (FDA) regulations 21 CFR 312.32, International Conference on Harmonization (ICH) guidelines, and European Clinical Trials Directive 2001/20/EC, or as per national regulatory requirements in participating countries. Adequate documentation must be maintained showing that Regulatory Authorities and IRBs/IECs have been properly notified.

SAEs must be reported within 24 hours, regardless of relationship, on a SAE Report Form to allow the Sponsor to take appropriate measures to address potential new risks in a clinical trial. The Investigator must report such events to the Sponsor immediately; under no circumstances should reporting take place more than 24 hours after the Investigator learns of the event.

The term sudden death should be used only when the cause is of a cardiac origin as per standard definition. The terms death and sudden death are clearly distinct and must not be used interchangeably. The study will comply with all local regulatory requirements and adhere to the full requirements of the ICH Guideline for Clinical Safety Data Management, Definitions and Standards for Expedited Reporting, Topic E2.

The SAE Report Form must be signed by the PI or assigned designee.

Other supporting documentation of the event may be requested by the safety department/pharmacovigilance contractor and should be provided as soon as possible.

All SAEs will be followed until satisfactory resolution as per Section [9.3 TYPE AND DURATION OF FOLLOW-UP OF SUBJECTS AFTER ADVERSE EVENTS](#).

